7.1.4 CYP1A2

CYP1A2 activity is calculated as the molar metabolic ratio of PX / CAF in plasma, both expressed in molar equivalent (nmol/L).

The conversion factor will be applied as follows:

PX	The molecular weight is 180.166 g/mol (Chemical Information Specialized Information Services RN:611-59-6). Therefore to convert PX in ng/mL to nmol/L the result in ng/mL is multiplied by 5.550.
CAF	The molecular weight is 194.193 g/mol. (Chemical Information Specialized Information Services RN:58-08-2). Therefore to convert CAF in ng/mL to nmol/L the result in ng/mL is multiplied by 5.150.

The converted results will be calculated to three decimal places and the ratio will be reported as a percentage with two decimal places.

If either of the PX or CAF concentration is LLOQ then the ratio will not be calculated.

7.1.5 CYP2A6

CYP2A6 activity is calculated in plasma as the metabolic ratio of trans-3' hydroxycotinine to cotinine, both expressed in molar equivalent (nmol/L) (Jacob et al. 2011).

The conversion factor will be applied as follows:

Cotinine	The molecular weight is 176.215 g/mol (Chemical Information Specialized Information Services RN:486-56-6). Therefore to transform cotinine from ng/mL to nmol/L, the result in ng/mL will be multiplied by 5.675.
Trans-3'hydroxycotinine	The molecular weight is 192.217 g/mol (Chemical Information Specialized Information Services RN:34834-67-8). Therefore to transform trans-3' hydroxycotinine from ng/mL to nmol/L, the result in ng/mL is multiplied by 5.202.

The converted results will be calculated to three decimal places and the ratio will be reported as a percentage with two decimal places.

If either of the cotinine or trans-3'hydroxycotinine concentration is LLOQ then the ratio will not be calculated.

7.1.6 Laboratory Parameters

Values below the Lower LLOQ will be handled as described in Section 7.1, "Biomarkers".

7.2 Pharmacokinetic Parameters

The peak nicotine and cotinine plasma concentration (C_{peak}) and time to peak concentration (t_{peak}) will be obtained directly from the concentrations taken on Day 5. The weighted average concentration over 24 hours on Day 5 (C_{avg}) will be calculated by dividing the area under the curve from 0 to 24 h ($AUC_{0-24\text{ h}}$) by 24, where the $AUC_{0-24\text{ h}}$ is calculated using the linear trapezoidal rule.

Since the samples are taken whilst the subjects are smoking freely all samples must be non-missing for the parameters to be calculated as C_{peak} (and t_{peak}) could occur at any time.

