7.5.1.2 Plasma Nicotine and Cotinine

Nicotine and cotinine concentrations will be measured in plasma to evaluate the exposure to nicotine. For subjects in the SA arm, blood samples will be collected on Days 0 to 4, at comparable time points. No nicotine PK profile will be done for subjects in the SA arm on Day 5 and Day 6.

- On Day 0 to Day 4 (all study arms):

One blood sample for nicotine and cotinine will be drawn each day between 08:00 PM-09:30 PM.

- Nicotine/cotinine PK Profile on Day 5 and Day 6 (THS 2.2 and CC arms only):

In total, 9 blood samples will be drawn on Day 5. The first blood sample on Day 5 will be drawn within 15 minutes prior to the first product use (=T0). On Day 5, T0 will serve as a

Confidentiality statement: Data and information contained in this document are considered to constitute trade secrets and confidential commercial information, and the legal protections provided to such trade secrets and confidential information are hereby claimed under the provisions of applicable law. No part of this document may be publicly disclosed without the written consent of Philip Morris Products S.A.

reference for the time to peak concentration. An additional 8 blood samples will be drawn in 2-hour intervals after T₀. The last blood sample should be drawn no later than 11:00 PM, corresponding to the end of the product use period. At all time-points, if the subject wants to smoke around the time of the blood draw, he/she should smoke first and the blood will be drawn after the product has been used. Depending on the time of the first product use, it may be that fewer than 8 blood samples will be collected from a subject after T₀.

On Day 6, two blood samples will be drawn. The first one will be 20 hours after T₀ and the second blood sample will be 24 hours after T₀ (with T₀ being the time of the first product use on Day 5).

- On Day 5 and Day 6 (SA arm only):

On Day 5, one blood sample will be drawn between 08:00 PM-09:30 PM.

On Day 6, one blood sample will be drawn between 08:00 AM-09:30 AM.

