**Table 16: Assessment Windows**

Assessment	Nominal Time point(s)	Window
CO breath test	Day -2 and Day 6 Morning (Days -1 to 5)	Irrespective of product use To be done within 15 minutes prior to product use (for THS 2.2 and CC arms) or between 08:00 AM and 09:30 AM (SA arm)
	Day -1 to Day 5	Between 12:00 PM and 01:30 PM, 04:00 PM and 05:30 PM, and 08:00 PM and 09:30 PM
Assessment of Cough	Day 0 to 6	To be done prior to smoking/product use but not later than 10:00 AM.
MNWS Questionnaire	Day 0 to 6	To be done prior to product use but not later than 10:00 AM
QSU-brief questionnaire	Day -1 to 5	08:00 PM to 11:00 PM
MCEQ questionnaire	Day -1 to 5	08:00 PM to 11:00 PM
Nicotine and cotinine in plasma	Day 0 to Day 4 (all study arms) between 08:00 PM and 09:30 PM	
	Day 5 (THS 2.2 and CC arms) within 15 minutes before first product use (T_0): then additional blood samples at 2 hour intervals from T_0 until 11:00 PM.	Each sample has a 5 minute time window
	Day 6 (THS 2.2 and CC arms): 20 and 24 h after T_0 of Day 5 Day 5 and Day 6 (SA arm): On Day 5, between 08:00 PM and 09:30 PM. On Day 6, between 08:00 AM and 9:30 AM.	5 minute time window
COHb blood Sampling	Days -1 to 4 Morning sample on Day 5	8:00 PM to 09:30 PM Within 15 minutes prior to product use (for THS 2.2 and CC arms) or between 08:00 AM and 09:30 AM (SA arm)
	Day 5 other samples	Between 12:00 PM and 01:30 PM, 04:00 PM and 05:30 PM, and 08:00 PM and 09:30 PM

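### The all-samples rule in SAP 7.2 does not fit a schedule that expects fewer draws from later starters, and one missed draw voids Cpeak, tpeak and Cavg together

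*SAP*

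**What the plan says.** **Parameter rule.** SAP 7.2 takes Cpeak and tpeak directly from the Day 5 concentrations. Cavg is AUC0-24 divided by 24, with the AUC from the linear trapezoidal rule. Because subjects use product freely and the peak may fall at any time, "all samples must be non-missing for the parameters to be calculated". SAP 12.1.5 adds that missing data are in general not imputed.

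**Sampling in the THS 2.2 and CC arms.** Protocol 7.5.1.2 states "In total, 9 blood samples will be drawn on Day 5": one at T0, then an "additional 8 blood samples will be drawn in 2-hour intervals". It adds "The last blood sample should be drawn no later than 11:00 PM". Two more draws follow on Day 6, at 20 and 24 hours after T0. The same section then qualifies the count: depending on when first use occurs, "it may be that fewer than 8 blood samples will be collected from a subject" after T0.

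**T0.** Protocol 7.5.1.2 first attaches T0 to the blood draw taken up to 15 minutes before first use. It later describes T0 as "being the time of the first product use on Day 5".

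**The SAP's own schedules.** Table 16 asks for a pre-use draw, "then additional blood samples at 2 hour intervals from" T0 until 11:00 PM, and gives no count. Note i to the assessment schedule in SAP 16.1 fixes the number after T0 at eight.

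**Use of the parameters.** SAP 12.6.2.3 compares Cpeak and Cavg between THS 2.2 and CC by ANOVA, and tpeak by the Wilcoxon rank sum test, in tables labelled FAS.

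**The concern.** The protocol foresees shorter sample sets for some subjects. The SAP requires complete sets and does not say whether a draw that could not be taken before 11:00 PM counts as missing. A programmer working from note i and one working from Table 16 would analyse different subjects.

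Under the fixed-eight reading, whether a subject enters the PK comparison depends on the clock time of first product use on Day 5. That is behaviour after randomisation, in an open-label study with ad libitum use. The tables would still be labelled FAS while holding only the earliest starters.

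A second problem does not depend on the reading. The reason given for requiring complete data is that the peak may be missed. That reason bears on Cpeak and tpeak, but the rule also removes Cavg.

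**Working it through.** **Inputs.** Product use opens at 06:30 AM (Protocol 4.1). Up to eight draws follow T0 at 2-hour spacing, the last by 23:00, with further draws at T0 + 20 h and T0 + 24 h (Protocol 7.5.1.2). Each draw has a +5 minute window (Protocol Table 14).

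**Reproducing the planned nine.** Draws after T0: k = min(8, whole number of 2-hour steps in 23:00 − T0). For T0 = 06:30, 16.5 h / 2 h = 8.25, so k = 8, the last draw is at 22:30 and the Day 5 total is 9. This matches the protocol.

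**Latest T0 for a full set.** 23:00 − 8 × 2 h = 07:00. The span from 06:30 is 30 minutes.

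**Later starts.** The gap before the 20 h sample is 20 − 2k hours.

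| T0 | Draws after T0 | Day 5 total | Last Day 5 draw | Gap to 20 h sample |
|---|---|---|---|---|
| 06:30 | 8 | 9 | 22:30 | 4 h |
| 07:00 | 8 | 9 | 23:00 | 4 h |
| 07:01 | 7 | 8 | 21:01 | 6 h |
| 09:00 | 7 | 8 | 23:00 | 6 h |
| 09:01 | 6 | 7 | 21:01 | 8 h |
| 10:00 | 6 | 7 | 22:00 | 8 h |

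**How firm the cut-off is.** If T0 is first use, the cut-off on first use is 07:00. If T0 is the pre-use draw, first use may be as late as 07:00 + 15 min = 07:15. The +5 minute window moves the latest T0 to 06:55 if it must fit before 23:00, or to 07:05 if it may run past.

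**The two readings.** Against the fixed eight in note i, a subject with T0 at 07:30 has seven draws after T0, so one is absent and all three parameters are void. Against Table 16, the eighth draw (23:30) was never due, nothing is missing, and all three are calculated.

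**Size under the fixed-eight reading.** The documents give no distribution of first-use times, so the retained share f is an assumption, taken as equal in both arms. Subjects retained are 80f and 40f, and confidence intervals widen by 1/√f.

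| f (assumed) | THS 2.2 / CC | Interval width factor |
|---|---|---|
| 90% | 72 / 36 | 1.05 |
| 75% | 60 / 30 | 1.15 |
| 50% | 40 / 20 | 1.41 |
| 25% | 20 / 10 | 2.00 |

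**Sporadic missed draws, either reading.** A full set is 9 + 2 = 11 samples if the Day 6 draws count. With an assumed independent loss of 1% or 2% per draw, the share of subjects with at least one missing is 1 − 0.99^11 = 10.5% or 1 − 0.98^11 = 19.9%. For T0 between 06:30 and 07:00 the 20 h draw falls between 02:30 and 03:00 AM. If it counts among the required samples, missing it would also remove Cpeak and tpeak, which SAP 7.2 takes from Day 5 alone.

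**The case against.** The strongest reply is that SAP 7.2 asks for non-missing samples, not for eight. A draw that was never due need not be missing, the protocol itself allows for shorter sets, and Table 16 runs to 11:00 PM with no count. On that reading the two documents agree and nobody is dropped for starting late. This reading is available, but the SAP does not secure it, because note i in the same document says eight. A clarification is therefore needed.

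A reader might go further and infer that every subject first using product after 07:00 AM is lost, that this will be common, that those retained are the more dependent smokers, and that exclusion differs by arm. The documents do not support these as findings:

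- Loss of every such subject holds only under the fixed-eight reading. Even then the first-use cut-off may be 07:15, and the 11:00 PM limit is worded as a should.
- Several procedures precede first use on Day 5 (Protocol Table 14), so late starts are foreseeable, but nothing shows how frequent they are.
- FTND question 1 measures time from waking to the first cigarette, not clock time in a confined unit. If the queue for procedures sets T0, exclusion need not track dependence.
- A difference by arm is possible, since T0 follows randomisation, but no figure bears on it.

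It is also fair that the SAP gives a reason for complete data. Calculating Cpeak from a set with due draws missing could understate it, so a general tolerance for missed draws on the peak parameters would be a trade-off rather than a correction. That reason does not extend to Cavg.

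**Conclusion.** The point stands as a self-contradiction in the SAP plus a rule broader than its stated reason. A full set requires T0 at or before 07:00 AM, with the few minutes of latitude shown above. Whether later starters are excluded depends on which of the SAP's two schedules is followed. The number affected and any direction of bias cannot be determined; the retained shares and per-draw loss rates are illustrations only, and random loss would cost precision rather than create selection.

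The reach is limited. These are secondary, descriptive PK endpoints, and no primary endpoint is touched. Nicotine exposure is also compared without this rule, through the Day 5 plasma sample closest to 08:00 PM (SAP 12.6.2.2) and urinary nicotine equivalents (SAP 12.6.2.1). The change should be made, but the study's main conclusion does not depend on it.

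**What to change.** In SAP 7.2:

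1. Define the required samples as all draws due by 11:00 PM given the subject's T0, and align note i in SAP 16.1 with Table 16.
2. For Cpeak and tpeak, require the due Day 5 samples only.
3. Calculate AUC0-24 and Cavg by the linear trapezoidal rule on actual times, including the 20 h and 24 h samples, and do not void them for a single missed interior draw (one with a draw on either side).
4. Use one definition of T0 throughout.
5. Report the number of subjects analysed per arm for each parameter.
6. Keep the analysis restricted to complete sets as a sensitivity analysis.

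The cost is SAP wording and minor programming. The downside is that late starters (T0 from just after 07:00 to 11:00 AM) have 6 to 8 hours between their last Day 5 draw and the 20 h sample instead of 4, so their AUC is slightly less precise. Their last due draw can also precede 11:00 PM by almost 2 hours (21:01 for T0 at 07:01), against at most 30 minutes in a full set, so a late peak could go unseen. The sensitivity analysis would show whether either matters.

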7.3 Questionnaires

All used questionnaires, except the cough and HST questionnaires, are available as a validated questionnaire in Japanese. The cough and HST questionnaires will be forward-translated and back-translated with subsequent independent verification.

7.3.1 Fagerström Test for Nicotine Dependence (FTND)

The FTND will be used in its revised version (Heatherton et al 1991), as updated in 2012 (Fagerström et al. 2012). These questions are to be answered by the subject themselves. It is conducted at Screening only to determine subject's dependence on nicotine.

Table 3 describes the six questions the questionnaire consists of, and the scores associated with each question.

The FTND total score will be derived by summing the individual item scores if all items are non-missing, otherwise the total score will be set to missing. For the FTND total score, descriptive statistics and frequency tables according to the following classification will be provided (Fagerström et al. 2012):

Mild	0 – 3
Moderate	4 – 6
Severe	7 – 10

Table 3: Scoring for the Fagerstrom Test for Nicotine Dependence

	FTND Question	Response	Score
1	How soon after you wake up do you smoke your first cigarette?	▪ Within 5 minutes	3
		▪ 6 to 30 minutes	2
		▪ 31 to 60 minutes	1
		▪ After 60 minutes	0
2	Do you find it difficult to refrain from smoking in places where it is forbidden?	▪ Yes	1
		▪ No	0
3	Which cigarette would you hate most to give up?	▪ The first one in the morning	1
		▪ Any other	0
4	How many cigarettes per day do you typically smoke?	▪ 10 or less (up to ½ pack)	0
		▪ 11 to 20 (a little more than ½ pack, up to a full pack)	1
		▪ 21 to 30 (a little more than a pack, up to 1½ packs)	2
		▪ 31 or more (more than 1½ packs)	3

**Table 3: Scoring for the Fagerstrom Test for Nicotine Dependence**

	FTND Question	Response	Score
5	Do you smoke more frequently during the first hours after waking than during the rest of the day?	▪ Yes	1
		▪ No	0
6	Do you smoke if you are so ill that you are in bed most of the day?	▪ Yes	1
		▪ No	0

7.3.2 Questionnaire of Smoking Urges-Brief (QSU-brief)

The QSU-brief (Cox et al. 2001) is a self-reported questionnaire completed daily from Day -1 to Day 5 between 08:00 PM and 11:00 PM.

The QSU-brief consists of 10 items as presented in Table 4.

Table 4: Questionnaire of Smoking Urges Brief - Questions and Factors

	Question	Factor
1	I have a desire for a cigarette right now	1
2	Nothing would be better than smoking a cigarette right now	2
3	If it were possible, I probably would smoke now	1
4	I could control things better right now if I could smoke	2
5	All I want right now is a cigarette	2
6	I have an urge for a cigarette	1
7	A cigarette would taste good now	1
8	I would do almost anything for a cigarette now	2
9	Smoking would make me less depressed	2
10	I am going to smoke as soon as possible	1

All items will be rated on a 7-point scale, ranging from 1 (strongly disagree) to 7 (strongly agree). Higher scores indicate a higher urge to smoke.

Two factor scores and a total score will also be derived (Cox et al. 2001). Each factor is a subset that includes 5 of the 10 questions as defined in Table 4. Factor 1 represents the desire and intention to smoke with smoking perceived as rewarding, while Factor 2 represents an anticipation of relief from negative effect with an urgent desire to smoke.

The factors and total scores will be calculated by averaging non-missing item scores if at least 50% are non-missing, otherwise the factor or total score will be set to missing.

7.3.3 Modified Cigarette Evaluation Questionnaire

The MCEQ (Cappelleri et al. 2007) will be completed by the subject him/herself daily from Day -1 to Day 5 between 08:00 PM and 11:00 PM. On Day -1 and Day 0, all subjects will complete the questionnaire. From Day 1 onwards it will be completed by

subjects in the CC and THS 2.2 arms only to assess the degree to which subjects experience the reinforcing effects of smoking.

The MCEQ consists of 12 items as presented in Table 5.

Table 5: Modified Cigarette Evaluation Questionnaire - Questions and Subscales

	Question	Subscale
1	Was smoking satisfying?	Smoking Satisfaction
2	Did cigarettes taste good?	Smoking Satisfaction
3	Did you enjoy the sensation in your throat and chest?	Enjoyment of Respiratory Tract Sensations
4	Did smoking calm you down?	Psychological Reward
5	Did smoking make you feel more aware?	Psychological Reward
6	Did smoking make you feel less irritable?	Psychological Reward
7	Did smoking help you concentrate?	Psychological Reward
8	Did smoking reduce your hunger for food?	Psychological Reward
9	Did smoking make you dizzy?	Aversion
10	Did smoking make you nauseous?	Aversion
11	Did smoking immediately relieve your craving for a cigarette?	Craving Reduction
12	Did you enjoy smoking?	Smoking Satisfaction

Items are assessed on a 7-point scale, ranging from 1 (not at all) to 7 (extremely). Higher scores indicate greater intensity on that scale.

The subscales scores will be derived by averaging the individual non-missing item scores if at least 50% are non-missing, otherwise the subscale score will be set to missing.

7.3.4 Minnesota Nicotine Withdrawal Scale (revised edition) Questionnaire

The MNWS (Hughes and Hatsukami 2008) is a 24 hour recall that will be completed by the subject him/herself daily on Day 0 to Day 6 prior to product use to reflect the previous days experience. Therefore although it is collected on Days 0 to 6 it will be reported as Days -1 to 5. Only the self-reported part of the MNWS will be used.

The self-reported part of the MNWS consists of the following 15 items which are rated over the last 24 hours on a scale of 0 to 4 (see Table 6). Higher scores indicate greater intensity on that scale.

The total scores will be derived by summing the individual item scores if all items are non-missing, otherwise the total score will be set to missing. The first total score calculated by summing the first 9 items is based on validated items, the second score is based on 6 extra items which are thought to have an impact on withdrawal but have not been validated.

**Table 6: Minnesota Nicotine Withdrawal Scale (Revised Edition)
Questionnaire Scores**

	Question	Total Score
1	Angry, irritable, frustrated.	1 and 2
2	Anxious, nervous.	1 and 2
3	Depressed mood, sad.	1 and 2
4	Desire or craving to smoke.	1 and 2
5	Difficulty concentrating.	1 and 2
6	Increased appetite, hungry, weight gain.	1 and 2
7	Insomnia, sleep problems, awakening at night.	1 and 2
8	Restless.	1 and 2
9	Impatient.	1 and 2
10	Constipation	2
11	Dizziness	2
12	Coughing	2
13	Dreaming or nightmares	2
14	Nausea	2
15	Sore throat	2

7.3.5 Human Smoking Topography Questionnaire

The HST questionnaire will be completed on Days 0 and 4 by all subjects smoking CC that are compatible with the HST SODIM[®] device (i.e., non-slim CC) to evaluate the impact of the use of the HST SODIM[®] device.

The HST questionnaire has 5 items rated on a 5-point Likert scale (strongly agree, agree, neither agree nor disagree, disagree and strongly disagree). The items are:

1. The smoking of the conventional cigarettes/products is different with the device.
2. You enjoy smoking with the device as much as without it.
3. The taste of the conventional cigarettes/products is different with the device.
4. The device is easy to use.
5. Your smoking is disturbed by the device.

7.3.6 Cough Assessment

Subjects will be asked to assess the respiratory symptom ‘cough’ using a VAS, three Likert scale questions, and one open ended question on a daily basis during the confinement period (on Day 0 to Day 6) prior to start of product use/smoking and no later than 10:00 AM. Although the symptoms are assessed on Days 0 to 6 the data reflects the subjects respiratory symptoms from the previous day (Days -1 to Day 5) and therefore will be reported as Days -1 to Day 5 .

Subjects will be asked if they have experienced a regular need to cough, e.g., whether they have coughed several times in the previous 24 hours prior to assessment. If the answer is ‘yes’, subjects will be asked to complete questionnaire.

The VAS will assess how bothersome cough is to the subject ranging from ‘not bothering me at all’ to ‘extremely bothersome’, and this will be given a numeric value between 0 and 100, measured on a 100 mm scale.

Subjects will also be asked to assess the intensity and frequency of cough and the amount of sputum production on Likert scales as presented in **Table 7**.

Table 7 : Cough Assessment Likert Scales

	Question	Likert Scale
1	The intensity of cough	1 = very mild 2 = mild 3 = moderate 4 = severe 5 = very severe
2	The frequency of cough	1 = rarely 2 = sometimes 3 = fairly often 4 = often 5 = almost always
3	The amount of sputum production	0 = no sputum 1 = a moderate amount of sputum; 2 = a larger amount of sputum; 3 = a very large amount of sputum.

7.4 Human Smoking Topography Assessment

The HST SODIM[®] device measures and records the flow and other per-puff parameters listed below (**Table 8**). From the per-puff parameters, the per-cigarette parameters shown below will be derived (representing average values or totals per cigarette (**Table 9**)). Prior to calculation of the per-cigarette parameters, the topography data will be processed through analysis software. Only data that are able to be processed by the software will contribute to the per-cigarette parameters and will be part of the study database.

Table 8: HST- Per-Puff Parameters

Description	Variable	Unit
Puff number	Ni	
Puff volume	Vi	mL
Puff duration	Di	S
Average flow [Vi/Di]	Qmi	mL/s
Peak flow	Qci	mL/s
Inter puff interval	li	S
Sum of li and Di	DFi	S
Work [INT Pmi*FinalFlow*dt]	Wi	mJ
Average pressure drop	Pmi	mmWG
Peak pressure drop	Pci	mmWG
Average resistance [Pmi/Qmi]	Rmi	mmWG/mL/s
Peak resistance [Pci/Qci]	Rci	mmWG/mL/s

Table 9: HST - Per-Cigarette Parameters

Description	Variable	Formula	Unit
Total number of puffs	NPC	$\sum Ni$	
Total puff volume	TVOL	$\sum Vi$	mL
Average puff volume	AvgVi	$\sum Vi / NPC, i=1 \dots NPC$	mL
Average puff duration	AvgDi	$\sum Di / NPC, i=1 \dots NPC$	s
Total puff duration	TDi	$\sum Di$	s
Average flow	AvgQmi	$\sum Qmi / NPC, i=1 \dots NPC$	mL/s
Average Peak flow	AvgQci	$\sum Qci / NPC, i=1 \dots NPC$	mL/s
Total inter puff interval	Tli	$\sum li$	s
Average inter puff interval	Avgli	$\sum Qci / NPC, i=1 \dots NPC$	s
Total smoking duration	TDFi	$\sum DFi$	s
Total Work	TWi	$\sum Wi$	mJ
Average Work	AvgWi	$\sum Wi / NPC, i=1 \dots NPC$	mJ
Average pressure drop	AvgPmi	$\sum Pmi / NPC, i=1 \dots NPC$	mmWg
Average Peak pressure drop	AvgPci	$\sum Pci / NPC, i=1 \dots NPC$	mmWg
Smoking Intensity	SMINT	TVOL/TDFi	mL/s
Puffing Time Index	PTI	$(100*TDi)/TDFi$	%
Puff Frequency	PFeq	$NPC/(TDFi/60)$	puffs/min

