12.6.3.2 Human Smoking Topography Parameters

The HST assessments will take place on Day 0, Day 1 and Day 4 in the THS 2.2 and CC arms only, if CC are compatible with the HST SODIM[®] device.

The per puff parameters are shown in **Table 8** and the per cigarette parameters are shown in **Table 9**.

The per-cigarette parameters derived from the HST assessments will be summarized along with their changes from baseline. The per-puff and per-cigarette parameters will be listed. In addition the product mean and 95% CI per cigarette parameters will be presented graphically.

The per-cigarette parameters will be analyzed on Days 1 and 4 separately using an ANCOVA model on the log-transformed HST parameter with terms for log-transformed baseline score, sex, average daily CC consumption over the last 4 weeks as reported during screening, product. No adjustment will be made for multiple comparisons.

The SAS code will be the same as described in Section **12.6.1.1 “Primary Biomarkers of Exposure in 24 hour collection”**.

LS means for each product along with the ratio (THS 2.2 : CC) and 95% CI will be presented in the tables.

All figures, summaries and analyses will be performed on the FAS.

The data will be presented in the below outputs, the TFL number refers to the TFL number in the accompanying TFL shell document:

TFL number	Title
FIGURES	
15.1.2.39	HST per Cigarette Parameters Arithmetic Mean and 95% CI– FAS
TABLES	
15.2.4.63	Descriptive Statistics of HST Parameters per Cigarette – FAS
15.2.4.64	Analysis of HST per Cigarette – FAS
LISTINGS	
15.3.7.1	Listing of HST Assessments

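### The SAP and protocol topography tables define the average inter-puff interval with the formula for average peak flow

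*SAP*

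**What the plan says.** SAP Section 7.4 defines the topography variables in two steps. Table 8 lists quantities recorded for each puff, and Table 9 lists quantities per cigarette. The link between them is explicit: "From the per-puff parameters, the per-cigarette parameters shown below will be derived".

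In Table 8, "Inter puff interval" is the variable Ii, in seconds, and peak flow is Qci, in mL/s. In Table 9, the row "Average inter puff interval" (Avgli) has the formula ∑Qci/NPC, i=1…NPC, with unit s. The divisor NPC is the row "Total number of puffs", printed as ∑Ni, where Table 8 labels Ni as the puff number.

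Protocol Section 7.8.1.1 (Tables 4 and 5) gives the same definitions and the same two formulas. SAP Section 9, which lists departures from the protocol analysis, mentions neither.

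SAP Section 5.3 names the average inter-puff interval among the exploratory topography endpoints. SAP Section 12.6.3.2 then says: "The per-cigarette parameters will be analyzed on Days 1 and 4 separately using an ANCOVA model on the log-transformed HST parameter". Results are to be presented as THS 2.2 : CC ratios with 95% confidence intervals.

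**The concern.** The formula for the interval contains no interval. It averages peak flow, a different quantity in a different unit, and duplicates another row of the same table. Table 9 is the only written specification of this parameter in the SAP, and the protocol carries the same line, so a programmer or a quality-control check working from either document would implement the wrong variable or verify against it.

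At stake is one pre-specified exploratory endpoint. Time between puffs is part of describing how smokers use THS 2.2 compared with cigarettes. Under the printed formula that description would be missing, and a second copy of the peak-flow result would stand in its place.

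**Working it through.** There is no stated figure to reproduce, so the check is one of definitions and units.

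**Inputs.** From SAP Table 8: Ii (interval, s), Di (puff duration, s), Qci (peak flow, mL/s), and DFi = Ii + Di. From SAP Table 9: the formulas and units below. Protocol Tables 4 and 5 agree.

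| Table 9 row | Formula printed | Unit printed | Unit the formula gives |
|---|---|---|---|
| Average peak flow (AvgQci) | ∑Qci/NPC | mL/s | mL/s |
| Total inter-puff interval (TIi) | ∑Ii | s | s |
| Average inter-puff interval (Avgli) | ∑Qci/NPC | s | mL/s |

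The first and third rows have one formula and two incompatible units. The row between them uses the right variable, Ii, which points to a copying slip.

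**Illustration.** All values are assumed, and none is in the documents: 10 puffs, each with interval 20 s, duration 2 s and peak flow 40 mL/s. NPC is taken as the count, 10.

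- As printed: ∑Qci/NPC = (10 × 40)/10 = 40, labelled s.
- With the interval variable: ∑Ii/NPC = (10 × 20)/10 = 20 s.

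**Internal check.** Because DFi = Ii + Di, total smoking duration divided by NPC should equal average interval plus average puff duration. Total duration is 10 × (20 + 2) = 220 s, and 220/10 = 22 s. The corrected formula gives 20 + 2 = 22. The printed one gives 40 + 2 = 42.

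**Effect on the analysis.** The same formula would apply to the Day 0 baseline and to Days 1 and 4. Outcome and baseline covariate would then both equal those for average peak flow, and the model terms are the same, so the ratio and confidence interval would be the peak-flow ones exactly.

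**The puff count.** If Ni is the ordinal 1, 2, …, n, then ∑Ni = n(n+1)/2, which is 55 for the assumed 10 puffs. If Ni is 1 for each puff, ∑Ni = 10. The averages in Table 9 run over i=1…NPC. With NPC = 55 that index would run past the tenth and last puff, so only the count fits.

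**The case against.** The best defence is that the intent is plain. Name, symbol and unit all say interval, the adjacent total is correct, and the intended value can be recovered by dividing the total interval by the number of puffs. There is also a processing step: "the topography data will be processed through analysis software", and protocol Section 7.8.1.1 has the sponsor's topography group validate the data beforehand. The software may well compute the interval correctly. This stands as a limit on what can be claimed: the documents do not show that wrong values would be reported. It does not cure the text. No other algorithm is given, so either the software follows the table and the result is wrong, or it does not and the SAP misdescribes the analysis.

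The reach is small, which also stands. The endpoints are exploratory, analysed without multiplicity adjustment, and outside the success criterion in SAP Section 5.5.2.

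A reader might go further and infer that NPC is wrong too, so that 10 of the 17 rows (NPC itself, the eight averages and puff frequency) are distorted, the averages by a factor 2/(n+1) that would not cancel between arms with different puff counts. The documents do not support this as an established error. It requires Ni to be the ordinal, whereas the row name, the index i=1…NPC and the SAP's unit of puffs per minute for puff frequency all treat NPC as a count. Any figure for its size would also rest on assumed puff counts. What remains is ambiguous notation that deserves one clarifying line.

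**Conclusion.** The point holds for the average inter-puff interval. The printed formula is average peak flow under any reading of NPC, the error appears in both documents, and nothing in SAP Section 9 corrects it. It is an error in an analysis rule for a listed endpoint, not merely a typographical blemish in background text.

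Its certain size is one of 17 per-cigarette parameters and its analyses on Days 1 and 4. The four primary biomarkers and the study's success criterion are untouched. The conclusion rests on the definitions in the tables alone; the numerical example only illustrates it. Whether reported values would be wrong depends on software not described in the documents.

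**What to change.** 1. In SAP Table 9 and protocol Table 5, set Avgli = ∑Ii/NPC, i=1…NPC, unit s. Dividing by NPC follows the convention of every other per-puff average in the table. Dividing by a number of intervals would need a definition that neither document gives.
2. Add one line to both tables stating that NPC is the count of puffs recorded for the cigarette.
3. Record the correction in SAP Section 9.
4. Check the software output against these definitions. A quick test is that average interval plus average puff duration equals total smoking duration divided by NPC.

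The cost is one formula and one clarifying line in each table, plus one output check. No new data and no change to the model are needed.
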